## 6.5.2. Additional considerations

### 6.5.2.1. Exclusion of implausible solicited Adverse Event

Some local and systemic adverse events will be directly measured by the subject and will not be subject to a reconciliation process, even if they are biologically implausible, therefore these implausible measurements will be removed from the analysis but included in listings. Implausible measurements are summarized in the [Table 4](#) below:

**Table 4 Implausible Solicited Adverse Events**

Parameter	Implausible measurements
Body temperature	$\leq 33^{\circ}\text{C}$ or $\geq 42^{\circ}\text{C}$
Redness	$\geq 900$ mm $< 0$ mm
Swelling	For subjects $\geq 6$ years: $\geq 500$ mm Measurements $< 0$ mm

### 6.5.2.2. Solicited Adverse Events

All analyses will be based on the Solicited Safety set.

Solicited adverse events will be reported from Day 1 to Day 7 using structured diaries. The analyses of solicited adverse events will be done based on the interval: Day 1-Day 7.

Temperature (in this study preferred location to measure the temperature is oral cavity or axilla) will be scored at GSK Biologicals as follows:

0:  $< 37.5^{\circ}\text{C}$

1:  $37.5\text{-}37.9^{\circ}\text{C}$

2:  $38.0^{\circ}\text{C}\text{-}38.9^{\circ}\text{C}$

3:  $\geq 39.0^{\circ}\text{C}$

**CONFIDENTIAL**207759 (NTHI MCAT-008)  
Statistical Analysis Plan Amendment 1 Final

In addition, body temperature will be broken down by 0.5 °C increments:

- <36.0,
- 36.0 - 36.4
- 36.5 - 36.9
- 37.0 - 37.4
- 37.5 - 37.9
- 38.0 - 38.4
- 38.5 - 38.9
- 39.0 - 39.4
- 39.5 - 39.9
- $\geq 40.0^{\circ}\text{C}$

Fever, defined as a body temperature of  $\geq 37.5^{\circ}\text{C}$  irrespective of route of measurement, will be integrated to the summaries as a systemic adverse event.

For the definition of the grading to be reported in the analysis, please refer to Section [6.5.2.2.1](#) and [6.5.2.2.2](#).

**6.5.2.2.1. Grading definition for Local solicited Adverse Events.**

Local AE	Grading	Collection period
Pain at injection site	0: None 1: Mild 2: Moderate 3: Severe	Day 1 - Day 7 after any vaccination
Redness at injection site	0: < 20 mm diameter 1: $\geq 20$ mm to $\leq 50$ mm diameter 2: > 50 mm to $\leq 100$ mm diameter 3: > 100 mm diameter	Day 1 - Day 7 after any vaccination
Swelling at injection site	0: < 20 mm diameter 1: $\geq 20$ mm to $\leq 50$ mm diameter 2: > 50 mm to $\leq 100$ mm diameter 3: > 100 mm diameter	Day 1 - Day 7 after any vaccination

**CONFIDENTIAL**

207759 (NTHI MCAT-008)

Statistical Analysis Plan Amendment 1 Final

**6.5.2.2. Grading definition for General solicited Adverse Events.**

General AE	Grading	Collection period
Headache	0: None 1: Mild 2: Moderate 3: Severe	Day 1 - Day 7 after any vaccination
Fatigue	0: None 1: Mild 2: Moderate 3: Severe	Day 1 - Day 7 after any vaccination
Gastrointestinal symptoms (nausea, vomiting, diarrhoea and/or abdominal pain)	0: None 1: Mild 2: Moderate 3: Severe	Day 1 - Day 7 after any vaccination
Myalgia	0: None 1: Mild 2: Moderate 3: Severe	Day 1 - Day 7 after any vaccination
Chills	0: None 1: Mild 2: Moderate 3: Severe	Day 1 - Day 7 after any vaccination
Fever	0: < 37.5°C 1: 37.5°C to 37.9°C 2: 38.0°C to 38.9°C 3: ≥ 39.0°C	Day 1 - Day 7 after any vaccination

**6.5.2.3. Unsolicited Adverse Events**

All analyses will be based on the Exposed and Unsolicited Safety set.

All the unsolicited adverse events occurring during the study, judged either as related or not related to vaccination by the investigator, will be recorded. The original verbatim terms used by investigators to identify adverse events in the CRFs will be mapped to preferred terms using the MedDRA dictionary. The unsolicited adverse events will then be grouped by MedDRA preferred terms into frequency tables according to system organ class. Adverse events judged by the investigator as related to study vaccine will be summarized by vaccine group, according to system organ class and preferred term within system organ class. When an unsolicited adverse event occurs more than once for a subject, the maximal severity will be counted.

Only vaccine-emergent adverse events will be analysed, i.e., excluding those after a subject has given informed consent but before first vaccination. The selection of unsolicited adverse events and the assignment to time intervals will be done by day of onset and not by days ongoing/persisting.

The analysis of unsolicited adverse events is summarised according to the following categories:

**CONFIDENTIAL**207759 (NTHI MCAT-008)  
Statistical Analysis Plan Amendment 1 Final***After any and each vaccination***

- Unsolicited adverse events with onset within 30 days after vaccination
- Related unsolicited adverse events with onset within 30 days after vaccination
- Grade 3 unsolicited adverse events with onset within 30 days after vaccination
- Grade 3 related unsolicited adverse events with onset within 30 days after vaccination

***By Epoch and overall***

- Serious unsolicited adverse events
- Related serious unsolicited adverse events
- Potential immune-mediated diseases (pIMDs)
- Fatal unsolicited adverse events
- Related fatal unsolicited adverse events
- Unsolicited adverse events leading to hospitalization
- Unsolicited adverse events leading to premature withdrawal from study

**6.5.2.4. Combined Solicited and Unsolicited Adverse Events**

A summary of subjects with all combined solicited (regardless of their duration) and unsolicited adverse events will be provided. Solicited adverse events will be coded by MedDRA as per the following codes

Solicited symptom	Preferred term code	Corresponding Preferred term decode
Pain	10022086	Injection site pain
Redness	10022061	Injection site erythema
Swelling	10053425	Injection site swelling
Headache	10019211	Headache
Fatigue	10016256	Fatigue
Gastrointestinal symptoms	10017944	Gastrointestinal disorder
Myalgia	10028411	Myalgia
Chills	10008531	Chills
Fever	10016558	Pyrexia

For clintrial.gov and EudraCT posting purposes, a summary of combined solicited and unsolicited non-serious adverse events will be produced by System Organ Class and preferred terms and according to occurrence of each event.

**6.5.2.5. Clinical Safety Laboratory Investigations**

Not Applicable.

**CONFIDENTIAL**207759 (NTHI MCAT-008)  
Statistical Analysis Plan Amendment 1 Final**6.5.2.6. Concomitant Medication**

Medications will be coded using the GSKDRUG dictionary.

The frequencies and percentages of subjects reporting concomitant medications will be tabulated by vaccine group for each study dose and across doses. The following concomitant medication categories will be considered in the summaries

- All concomitant vaccines or medications or products, associated with an AE, except vitamins and dietary supplements, administered during the entire study period following the first dose of study vaccine (Day 1 to Day 721).
- Prophylactic medication (i.e. medication administered in the absence of ANY symptom and in anticipation of a reaction to the vaccination).

E.g. an anti-pyretic is considered to be prophylactic when it is given in the absence of fever and any other symptom, to prevent fever from occurring.

- Any concomitant medications/products/vaccines relevant to a SAE/pIMD to be reported as per protocol or administered at any time during the study period for the treatment of a SAE/pIMD. In addition, concomitant medications relevant to SAEs and pIMD need to be recorded on the expedited Adverse Event report.

**7. ANALYSIS INTERPRETATION**

All safety and immunogenicity analyses are planned with the intention to estimate the safety and immune response after a third injection.

**8. CONDUCT OF ANALYSES****8.1. Sequence of analyses**

Description	Analysis ID	Disclosure Purpose (CTRS=public posting, SR=study report, internal)	Dry run review needed (Y/N)	Study Headline Summary (SHS) requiring expedited communication to upper management (Yes/No)	Reference for TFL
Final Analysis epoch 1	E1_01	SR	Y	Y	See references TFL TOC
Follow-up epoch analysis	E1_02	SR	Y		Y

**8.2. Statistical considerations for interim analyses**

No interim analysis is planned for this study. Data up to and including Day 541 (i.e. Visit 9) are considered ‘final’ and completed data, while the remaining 6 months open label safety data are considered long-term safety follow-up.

**CONFIDENTIAL**207759 (NTHI MCAT-008)  
Statistical Analysis Plan Amendment 1 Final**9. CHANGES FROM PLANNED ANALYSES**

Not Applicable.

**10. LIST OF FINAL REPORT TABLES, LISTINGS AND FIGURES**

The TFL TOC provides the list of tables/listings and figures needed for the study report. It also identifies the tables eligible for each analysis and their role (synopsis, in-text, post-text, SHS, CTRS,...). Note that all TFL aimed to be included as post-text are noted as post-text even if these are tabulation of individual data such as listing of SAE. The post-text material contains all source material for the study report and accordingly a post-text table may be redundant with an in-text table.

The following group names will be used in the TFLs:

Group order in tables	Group label in tables	T-domains	Group definition for footnote
1	Schedule 0-2-6	Schedule 1	Third dose at six months.
2	Schedule 0-2-12	Schedule 2	Third dose at one year.

The group names in the Protocol, Schedule 1 and Schedule 2, will be renamed as Schedule 0-2-6 and Schedule 0-2-12, respectively, in all the statistical analyses and in the study report.

**11.2. Standard data derivation****GSK legacy****11.2.1. Date derivation**

- SAS date derived from a character date: in case day is missing, 5 is used. In case day & month are missing, 30 June is used.
- Onset day for an event (AE, medication, vaccination, ...): the onset day is the number of days between the last study vaccination & the onset/start date of the event.

**CONFIDENTIAL**

207759 (NTHI MCAT-008)

Statistical Analysis Plan Amendment 1 Final

This is 0 for an event starting on the same day as a vaccination. See SAS date derived in case the start date of the event is incomplete.

- Duration: duration of an event is expressed in days. It is the number of days between the start & the stop dates + 1. Therefore, duration is 1 day for an event starting & ending on the same day.
- Association of an event to the primary epoch: an adverse event belongs to the primary epoch, if the onset date is before and including Visit 9 or the last contact date, whichever is coming first.

**11.2.2. Dose number**

- The study dose number is defined in reference to the number of study visits at which vaccination occurred. More specifically dose 1 refers to all vaccines administered at the first vaccination visit while dose 2 corresponds to all vaccinations administered at the second vaccination visit even if this is the first time a product is administered to the subject.
- Relative dose: the relative dose for an event (AE, medication, vaccination) is the most recent study dose given before an event. In case the event takes place on the day a study dose is given, the related dose will be that of the study dose, even if the event actually took place before vaccination. For instance, if an adverse event begins on the day of the study vaccination but prior to administration of the vaccine, it will be assigned to this dose. In case a study dose is not administered and an event occurs after the subsequent study dose (e.g. 3rd study dose), the relative dose of the event will be study dose associated to the subsequent study dose (e.g. dose 3).
- The number of doses for a product is the number of time the product was administered to a subject.
- The incidence per dose is the number of vaccination visits at which an event was reported among all vaccination visits.

**11.2.3. Demography**

- Age: age at the enrolment, computed as the number of units between the date of birth and the enrolment. Note that due to incomplete date, the derived age may be incorrect; this may lead to apparent inconsistency between the derived age and the eligibility criteria/the age category used for randomization.

- Conversion of weight to kg

The following conversion rule is used:

- Weight in Kilogram= weight in Pounds / 2.2
- Weight in Kilogram =weight in ounces / 35.2

The result is rounded to 2 decimals.

**CONFIDENTIAL**207759 (NTHI MCAT-008)  
Statistical Analysis Plan Amendment 1 Final

- Conversion of height to cm  
The following conversion rule is used:
  - Height in Centimetres = Height in Feet \* 30.48
  - Height in Centimetres = Height in Inch \* 2.54The result is rounded to the unit (i.e. no decimal).
- Conversion of temperature to °C  
The following conversion rule is used:
  - Temperature in °Celsius = ((Temperature in °Fahrenheit -32) \*5)/9The result is rounded to 1 decimal.
- Smoking status conversion  
Subjects reporting smoking status START DATE='Before' and STOP DATE='Before' will have value 'Former' (i.e., no smoker)  
Subjects reporting smoking status START DATE='Before' and STOP DATE='Ongoing' will have value 'Current' (i.e., smoker)

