- Male condom combined with a vaginal spermicide (foam, gel, film, cream or suppository), and/or progesterone alone oral contraceptive.

Adequate contraception does not apply to subjects of child bearing potential with same sex partners, or for subjects who are and will continue to be abstinent from penile-vaginal intercourse on a long term and persistent basis, when this is their preferred and usual lifestyle.

**Adverse event:** Any untoward medical occurrence in a patient or clinical investigation subject, temporally associated with the use of a medicinal product, whether or not considered related to the medicinal product.

An adverse event (AE) can therefore be any unfavourable and unintended sign (including an abnormal laboratory finding), symptom, or disease (new or exacerbated) temporally associated with the use of a medicinal product. For marketed medicinal products,

**CONFIDENTIAL**207759 (NTHI MCAT-008)  
Protocol Amendment 3 Final

this also includes failure to produce expected benefits (i.e. lack of efficacy), abuse or misuse.

|   |   |
|---|---|
| Alcoholism:                                | 
Alcoholism, also known as dependency on alcohol or alcohol addiction, is a chronic disease. The signs and symptoms of alcoholism include:
 
 
• A strong craving for alcohol.
 
• Continued use despite repeated physical, psychological, or interpersonal problems.
 
• The inability to limit drinking.
 
  |
| Blinding:                                  | 
A procedure in which one or more parties to the trial are kept unaware of the treatment assignment in order to reduce the risk of biased study outcomes. The level of blinding is maintained throughout the conduct of the trial, and only when the data are cleaned to an acceptable level of quality will appropriate personnel be unblinded or when required in case of a serious adverse event. In an observer-blind study, the subject and the site and sponsor personnel involved in the clinical evaluation of the subjects are blinded while other study personnel may be aware of the treatment assignment (see Section 5.3 for details on observer-blinded studies).
 |
| Current smoker:                            | 
A person who is currently smoking or who has stopped smoking within 6 months before study start.
   |

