| Eligible:                                  | 
Qualified for enrolment into the study based upon strict adherence to inclusion/exclusion criteria.
  |
| End of Study
(Synonym of End of Trial) | 
For studies without collection of human biologicals samples or imaging data EoS is the Last Subject Last Visit (LSLV).
 
For studies with collection of Human Biologicals Samples or imaging data, EoS is defined as the date of the last testing/reading released of the Human Biological Samples or imaging data, related to primary and secondary endpoints. EoS must be achieved no later than 8 months after LSLV.
   |
| Epoch:                                     | 
An epoch is a set of consecutive timepoints or a single timepoint from a single protocol. Epochs are defined to support a main purpose which is either to draw conclusions on subject participation or to draw a complete conclusion to define or precise the targeted label of the product. Supporting means that data
  |

**CONFIDENTIAL**207759 (NTHI MCAT-008)  
Protocol Amendment 3 Final

collected at the timepoints included in an epoch must be sufficient to fulfil the purpose of the epoch.

Typical examples of epochs are screening, primary vaccinations, boosters, yearly immunogenicity follow-ups, and surveillance periods for efficacy or safety.

|  |   |
|--|---|
| eTrack:   | GSK's tracking tool for clinical trials.  |
| Evaluable:  | Meeting all eligibility criteria, complying with the procedures defined in the protocol, and, therefore, included in the per-protocol analysis (see Sections 6.6.2 and 10.5 for details on criteria for evaluability).  |
| Former smoker:  | A person who stopped smoking for at least 6 months at the time of study start.  |
| Immunological correlate of protection:  | The defined immune response above which there is a high likelihood of protection in the absence of any host factors that might increase susceptibility to the infectious agent.   |
| Investigational vaccine:
(Synonym of Investigational Medicinal Product) | A pharmaceutical form of an active ingredient being tested in a clinical trial, including a product with a marketing authorisation when used in a way different from the approved form, or when used for an unapproved indication, or when used to gain further information about an approved use.  |

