**5.6.5. Smoking status**

Record the subject's smoking status (current or former smoker) in the eCRF. Refer to the [glossary of terms](#) for the definitions of current and former smoker.

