### **6.1. Demography**

#### **6.1.1. Analysis of demographics/baseline characteristics planned in the protocol**

Demographic and baseline characteristics such as age at enrolment, sex, race, ethnicity and smoking status will be summarised by study group using descriptive statistics, for the Exposed Set:

- Frequency tables will be generated for categorical variable such as sex, race, ethnicity, age category, smoking status;
- Mean, median, standard deviation, minimum and maximum will be provided for continuous data such as age and pack-years of smoking.

The following variables will be included in demography summary and listings:

- Age in year
- Age category: 40-59 y, 60-80y
- Gender: Male, Female
- Race: (all reported in e-CRF)
- Ethnicity: Hispanic or Latino, Not Hispanic nor Latino
- Pack-years of smoking
- Smoking status

While, additionally, the following vital signs will be tabulated as baseline characteristics:

- Height (cm)
- Weight (kg)
- Body temperature
- Heart rate
- Respiratory rate
- Systolic Blood Pressure
- Diastolic Blood Pressure,

**CONFIDENTIAL**207759 (NTHI MCAT-008)  
Statistical Analysis Plan Amendment 1 Final

Demographic table will be also presented for All enrolled set, if differs from ES.

The distribution of subjects enrolled among the study sites will be tabulated as a whole and per study group.

Withdrawal status will be summarised by group using descriptive statistics:

- The numbers of withdrawn subjects will be tabulated according to the reason for withdrawal;
- The number of subjects enrolled into the study as well as the number of subjects excluded from the different analysis sets will be tabulated.

No inferential analyses of demographic data are planned.

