**6.4.2. Additional considerations****6.4.2.1. Humoral Immunogenicity**

- Calculation of the GMCs will be performed by taking the anti-logarithm in base 10 (anti-log10) of the mean of the log10 ELISA concentration.
- Antibody concentrations below the assay cut-off will be given an arbitrary value of half the assay cut-off for the purpose of geometric mean concentration (GMC) calculation.
- A seronegative subject is defined as a subject whose antibody concentration is below the assay cut-off value (i.e. the ELISA lower limit of quantification). Specifically, the assay cut-off values are defined as follows:

*Anti-PD antibodies: 153 EU/mL*

*Anti-PE antibodies: 16 EU/mL*

*Anti-PilA antibodies: 8 EU/mL*

*Anti-UspA2 antibodies: 28 EU/mL*

Assay cut-off and unit might be subject to change during the study (e.g. in case of assay re-optimization, qualification, (re)validation or standardization). In this case, this will be documented in the clinical study report.

- A seropositive subject is defined as a subject whose antibody concentration is greater than or equal to the assay cut-off value (i.e. the ELISA lower limit of quantification).
- For a given subject and analysis of a given immunogenicity measurement, missing or unevaluable measurements will not be replaced.

**CONFIDENTIAL**207759 (NTHI MCAT-008)  
Statistical Analysis Plan Amendment 1 Final

- The percentage of seropositive subjects and associated two-sided 95% Clopper-Pearson [1] confidence intervals (CIs) will be computed by vaccine group at each visit.
- The 95% CIs for the difference between the percentages of seropositive subjects will be computed using Miettinen and Nurminen method [2] which has superior performance characteristics when rates are close to 0 or close to 1 and when compared to those formed from the Wald statistic.
- GMCs for each group and their ratios at each post-exposure timepoint will be calculated by fitting an ANCOVA model including the country, age category (40 - 59 years or 60 - 80 years) and smoking status (current or former smokers) as factors and pre-Dose 1 concentration (as covariate).

The SAS statements that will be used to calculate the adjusted GMC will be similar to:

```
PROC glm;
  BY timepoint antibody;
  CLASS country age smoking_status group;
  MODEL logtiter= log_baseline country age smoking_status group;
  LSMEANS group / tdiff stderr cl pdiff;
RUN;
```

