In addition, the GMRs for each group and their ratios between study visit (timepoints) and the baseline measure will be calculated by fitting an ANOVA model on the log10 of the titer ratio between a generic visit x and the baseline visit. This model will include the country, age category (40 - 59 years or 60 - 80 years) and smoking status (current or former smokers) as factors.

The SAS statements that will be used to calculate GMRs between timepoints will be similar to:

```
PROC glm;
  BY timepoint antibody;
  CLASS country age smoking_status group;
  MODEL log(titer_visitx/baseline)= country age
  smoking_statusgroup;
  LSMEANS group / tdiff stderr cl pdiff;
RUN;
```

The same approach will be used to compute GMRs with respect to the humoral immune response at Day 181 and at day 361: in these cases, baseline refers to, respectively, Day 181 and Day 361 concentration.

GMCs and GMRs will be obtained by exponentiating the estimate of the log-ratio for each group.

**CONFIDENTIAL**207759 (NTHI MCAT-008)  
Statistical Analysis Plan Amendment 1 Final**6.4.2.2. Cell Mediated Immunity**

- The frequency of **antigen-specific** CD4+ or CD8+ T-cells for each individual subject is calculated as the difference between the frequency of CD4+ or CD8+ T-cells producing at least 2 cytokines among IFN- $\gamma$ , IL-2, IL-13, IL-17, TNF- $\alpha$  and/or CD40L, upon *in vitro* stimulation with the antigen (induction condition) minus the frequency of CD4+ or CD8+ T-cells producing at least 2 cytokines upon *in vitro* stimulation in medium only (background condition). For descriptive statistics purposes, differences less or equal to zero (0) are imputed to 1.

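### The smoking-status rule in SAP 11.2.3 has no 6-month test, so a recent quitter can be labelled Former where the protocol says Current (minor)

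*SAP*

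**What the plan says.** The Protocol Glossary of Terms defines a current smoker as "A person who is currently smoking or who has stopped smoking within 6 months before study start" and a former smoker as "A person who stopped smoking for at least 6 months at the time of study start". Protocol 5.6.5 instructs sites: "Record the subject's smoking status (current or former smoker) in the eCRF", and refers them to those glossary definitions. Protocol Table 5 schedules this record at Visit 1 and again at Visit 9.

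The current SAP (Amendment 1), section 11.2.3, gives a conversion rule for subjects whose start code is Before. One branch reads "STOP DATE='Before' will have value 'Former' (i.e., no smoker" and the other "STOP DATE='Ongoing' will have value 'Current' (i.e., smoker". The SAP contains no other definition of smoking status. The March 2018 SAP has the same rule, and section 9 of the current SAP declares no change from the planned analyses.

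The variable is used in three places:

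- SAP 6.1.1, baseline characteristics: "Frequency tables will be generated for categorical variable such as sex, race, ethnicity, age category, smoking status".
- SAP 6.4.2.1, GMC ANCOVA: "smoking status (current or former smokers) as factors and pre-Dose 1 concentration (as covariate". Protocol 10.9.1 specifies the same factor.
- SAP 6.4.2.1, GMR ANOVA: "smoking status (current or former smokers) as factors".

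**The concern.** The two documents define one variable differently, and the difference falls on one identifiable group: people who stopped less than 6 months before study start. They can be enrolled, because Protocol 4.2 admits current or former smokers with at least 10 pack-years and Protocol 4.3 does not exclude recent quitters.

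If the SAP rule is programmed as it reads, such a subject stored with the Before stop code is counted as Former. The baseline table would then describe a population by a definition that the protocol does not use, and the adjustment factor would not be the one that the protocol specified. The derived value could also disagree with the status that the site recorded. Section 11.2.3 does not say what point in time Before refers to, or which of the two scheduled smoking records is used.

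**Working it through.** The plan states no figure on this point, so the main check is a comparison of text.

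**Side-by-side test**

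| Subject at study start | Protocol glossary | SAP 11.2.3 as written |
|---|---|---|
| Still smoking | Current | Current (Ongoing) |
| Stopped 3 months ago, stored as Before | Current | Former |
| Stopped 2 years ago, stored as Before | Former | Former |

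The definitions disagree only in the middle row.

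**How many subjects.** Let q be the share of enrolled subjects who stopped within 6 months. The documents do not give q, so 1% to 10% is assumed. The number affected is 200 × q.

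**Effect on the models.** Further assumptions, for illustration only: half the subjects are Current by the protocol definition; all recent quitters are coded Former; the true current-minus-former difference d is 0.1 or 0.3 log10; the residual SD is 0.83. The SD is borrowed for scale from Protocol 10.4. It is consistent with the power statement there: (0.83 × (1.645 + 1.282) / 0.256)² = 90.0, against the stated 90. Smoking coding does not enter that calculation.

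- Share of protocol-Current subjects among those coded Former: p = q / (0.5 + q).
- Current-former contrast as coded: d × (1 − p).
- Added residual variance: e = (0.5 + q) × p × (1 − p) × d².
- Relative rise in the standard error of the group comparison: √((0.83² + e) / 0.83²) − 1.

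Worked case, q = 10% and d = 0.3:

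- p = 0.10 / 0.60 = 0.167.
- Contrast = 0.3 × 0.833 = 0.25.
- e = 0.60 × 0.167 × 0.833 × 0.09 = 0.0075.
- Rise = √((0.6889 + 0.0075) / 0.6889) − 1 = 0.54%.

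| q (assumed) | Subjects of 200 | p | Contrast, d = 0.1 | Contrast, d = 0.3 | SE rise, d = 0.1 | SE rise, d = 0.3 |
|---|---|---|---|---|---|---|
| 1% | 2 | 0.020 | 0.098 | 0.294 | 0.01% | 0.06% |
| 2% | 4 | 0.038 | 0.096 | 0.288 | 0.01% | 0.13% |
| 5% | 10 | 0.091 | 0.091 | 0.273 | 0.03% | 0.30% |
| 10% | 20 | 0.167 | 0.083 | 0.250 | 0.06% | 0.54% |

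The smoking contrast shrinks by about 2% to 17%, but the SAP model code requests least-squares means for group only, so that contrast is not a planned output. Recent quitters are expected in equal proportion in both randomised groups, so recoding them does not systematically shift the group ratio.

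**The case against.** The strongest reply is that Before and Ongoing are stored category values, not calendar dates. The rule sits among unit conversions and may only relabel what the site entered. Sites enter status by the glossary, so if a glossary Current is stored as Ongoing, the SAP returns the protocol category and nobody is misclassified. The database specification is not in the documents, so this cannot be excluded. For that reason the point is conditional. The reply does not remove it: nothing in either document says that the codes carry the 6-month rule, and the SAP's own explanations of its two labels, no smoker and smoker, point to smoking at the time of recording.

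The other objections stand, and they limit what a reader should infer:

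- A reader might infer that subjects are certainly misclassified and the baseline table is wrong. The number of recent quitters is unknown and may be zero.
- A reader might infer that the variable on which the population was selected is compromised. Selection was on at least 10 pack-years (Protocol 1.2.1 and 4.2). Pack-years are calculated from the questionnaire and summarised separately, and the rule does not touch them.
- A reader might infer a threat to the trial's conclusions. The primary endpoints are safety and reactogenicity, and SAP 6.5 does not use smoking status. Between-group humoral comparisons are exploratory under SAP 6.4.1.1.2.
- A reader might assume that a 6-month stop-date rule can be applied to existing data. Protocol 5.6.5 and 5.6.6 name status, years smoked and number of cigarettes, but no quit date.

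**Conclusion.** The conflict in definition is real and undeclared. The SAP rule as written omits the protocol's 6-month window for a baseline characteristic and a model factor, and would label as Former any enrolled recent quitter stored as Before.

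The consequence is small. The count is not given; 2 to 20 of 200 rests entirely on the assumed 1% to 10%. The group comparison loses less than 0.6% in precision under the assumptions above and is not materially biased. The primary safety endpoints are unaffected. What is at stake is a correct baseline description and fidelity to the covariate that the protocol specified. Severity: minor.

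**What to change.** In SAP 11.2.3, replace the conversion rule with a statement that smoking status is the Visit 1 Current/Former value recorded in the eCRF under Protocol 5.6.5, by the glossary definition, and that this value is used for the baseline table and all ANCOVA and ANOVA models. Naming Visit 1 also settles which of the two scheduled records applies.

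If the stored Before and Ongoing codes already embed the 6-month rule, say so in the same place. Derive status from a stop date only if a quit date precise enough for a 6-month cut is collected.

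The cost is one line in the SAP and the matching program step. No new data are needed, because Protocol 5.6.5 already requires the recorded status. Sample size, power and alpha do not change.
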